Following successful completion of the run-in period, participants are randomly allocated (1:2) to either a group that is the attention control (**n=20**) or to the group that receives cognitive training (CT) intervention for a total of 16 weeks (**n=40**). Participants are not to be informed that they were assigned to "attention control" or "cognitive training" conditions; rather, individuals in both groups are told that the aim of the study is to determine whether participation in "computer learning activities" reduces the risk of falls and improves functional ability. Sealed envelopes, prepared in advance, assign the participants to one of the two groups. The randomization schedule is prepared by the consulting statistician using block randomization (blocks of 6) prior to the research team's initial visit to interested parties. This approach ensures that consent is obtained prior to disclosure of group assignment and persons consent to participate in the study, regardless of the group they are assigned to. The envelope is not opened until completion of the run-in procedure. The principal investigator, co-investigators and outcome assessors are blinded to allocation until the end of the trial.

Intervention

Cognitive training, also known as "brain training", involves scheduled completion of specific tests of executive function, visuospatial orientation and perceptual speed. The CT is completed using a web-based computer interface (Cognifit, Inc.), with task difficulty tailored to the participant's abilities. We will use the Cognifit research interface as it allows tailoring of the intervention to specific tasks selected by the research team.

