Participants assigned to the attention control condition are provided with programmatic activities that are designed to control for nonspecific treatment effects (computer use, interaction with study staff). Participants will engage in an equal number of sessions (3 sessions/week for 16 weeks) watching preselected healthy aging-related video content on the computer (e.g. NIH Senior Health videos on talking with your provider, taking medications safely, and making the most of a medical visit, how to exercise safely). Participants will be asked to briefly note any information gained from each video on a personal discussion board provided to them within the content module. We track sessions completed on a weekly basis and provide reminders as needed. Discontinuation of intervention is made on participant request.

8-, 16- and 20-week Assessments

A member of the research team blinded to intervention/control group assignment conducts participant outcome assessments at the 8-, 16- and 20-week time periods (see Table 2). These assessments occur in same setting and under similar conditions to baseline testing (e.g., same shoes are to be worn). Following the 20-week assessment, an exit interview is

completed in order to gain insight into the protocol's acceptability including participant perceptions of the CT intervention. Participant interviews use a semi-structured interview protocol as a guide to explore their experiences, overall perceived benefits, challenges and attitudes towards the study protocol. All interview sessions are digitally recorded.

ANALYSIS

All planned statistical analyses will be performed using intention-to-treat. The primary time point of interest in this analysis is the 16-week post-randomization outcome assessment; however, means, standard deviations and distributions will be used to describe the outcomes of interest at baseline, midpoint of active intervention phase and 4 weeks post completion of intervention (week 20 post-randomization). A value of $p<0.05$ will be considered statistically significant. Should there be significant differences between groups on baseline demographic variables despite randomization, we will examine the relationship between the variable and the outcome using sensitivity analyses.

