The primary outcome of interest in the proposed RCT is reduction number of falls and injurious falls (See Table 1) at the end of the intervention (16 weeks). We are also interested in the retention of effect 1-month post-intervention. Number of falls and injurious falls will be determined from fall calendar data. Between group differences will be assessed using Mann Whitney U test. Of secondary interest as outcome in this study is reduction in risk of fall which is determined by an increase in the 10M walking speed from baseline and an increase in the Balance test score from baseline. Between group differences will be assessed using Student's t-test. In exploratory analyses, we will examine the change in risk of fall over time using linear mixed models for longitudinal data. As secondary endpoints, we will measure cognitive outcomes (CANTAB), functional outcomes (walking Gill Disability, inertial sensor gait and turn measures, and ISway measures; See Table 1). Outcomes will be compared between groups using either t-tests or Mann-Whitney U tests as appropriate. In exploratory analyses, we will examine the change in outcome measures over time using linear mixed models for longitudinal data.

To better understand feasibility of the study, we will estimate the proportion of older adults found eligible for inclusion who actually agree to participate in such a study. Further, we will compare the characteristics of those who are willing to participate with those who are not. We will also evaluate numbers of study who complete the study protocol and note any differences in participant characteristics in those who drop out. We will also note the numbers of older adults who express interest in the study but are not eligible. To evaluate acceptability of the study procedures and intervention, transcripts of interview sessions will be digitally recorded and transcribed verbatim for descriptive content analysis.

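### Intention-to-treat is claimed for every analysis, but the named week-16 tests use observed values only, the fall count ignores days at risk, and no rule covers missing outcomes or incomplete calendars

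*Combined protocol and SAP*

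**What the plan says.** All of this is in the Analysis section unless noted.

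- Principle: "All planned statistical analyses will be performed using intention-to-treat". No analysis set is defined.
- Timing: "The primary time point of interest in this analysis is the 16-week post-randomization outcome assessment".
- Falls: the number of falls and injurious falls is taken from the calendars, and "Between group differences will be assessed using Mann Whitney U test". There is no person-time term.
- Fall risk (10M walk speed and balance score, both as increase from baseline): Student's t-test. Other secondary outcomes: t-test or Mann-Whitney U.
- Longitudinal models: "In exploratory analyses, we will examine the change in outcome measures over time using linear mixed models for longitudinal data". A parallel sentence covers fall risk. Both are exploratory.
- Dropout: the feasibility paragraph says the team will "note any differences in participant characteristics in those who drop out". There is no expected rate, no imputation and no missing-data sensitivity analysis. The one sensitivity analysis planned concerns baseline demographic imbalance.

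Under Outcomes, calendars are filled in daily with one of three letters and collected monthly over 4 months. In Table 2, fall risk, gait, sway and disability are measured before the intervention and at weeks 8, 16 and 20. Allocation is 1:2, with 20 control and 40 CT participants.

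**The concern.** The stated principle and the named methods do not meet. A two-sample test on week-16 values leaves out a randomised person who has none, unless a value is imputed, and no imputation is planned. That person's baseline and week-8 data then contribute nothing.

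A raw fall count has the same difficulty in another form. Someone who returns two of the four monthly calendars must either be left out, which departs from analysing everyone randomised, or be entered with the falls recorded so far, which treats unobserved weeks as free of falls. The plan does not choose.

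Differential loss is plausible, though not established. One arm does adaptive training and the other watches videos, and in either arm the intervention may stop at the participant's request. If loss differs, the effect estimate on the primary outcome partly reflects how long people were observed. If it does not, there is still a cost in precision, which matters at 60 participants.

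**Working it through.** **Stated figures.** The plan gives no power, effect size, SD, fall rate or dropout rate, so there is no power or sample-size calculation to reproduce. Its allocation figures agree with each other: 60/3 = 20, 2 × 60/3 = 40, and 60/6 = 10 blocks. Everything below uses 20 versus 40, a two-sided 0.05 level (the plan does not state sidedness) and assumed rates.

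**1. Falls, short calendars entered as raw counts, no true effect.** If a fraction d of an arm leaves at a uniformly distributed time, the mean observed fraction of follow-up is 1 − d/2. The apparent ratio, CT to control, is (1 − d_CT/2)/(1 − d_C/2).

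| Dropout control / CT | Apparent fall ratio |
|---|---|
| 20% / 20% | 0.90/0.90 = 1.00 |
| 10% / 20% | 0.90/0.95 = 0.947 |
| 10% / 30% | 0.85/0.95 = 0.895 |
| 30% / 10% | 0.95/0.85 = 1.118 |
| 10% / 50% | 0.75/0.95 = 0.789 |

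Simulation (4,000 trials per setting, negative binomial falls, shape 1, 16-week mean 0.5 to 2) agrees: 0.89-0.90 at 10%/30%, 1.11-1.12 at 30%/10%, and 0.99-1.00 at 20%/20%. Mann-Whitney type I error was 0.045-0.048 at 20%/20%. At 10%/30% it was 0.052-0.067, with false positives favouring CT at 0.042-0.056 against a nominal 0.025. Dividing by observed time brought the 10%/30% ratio back to 0.99-1.00.

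**2. Continuous outcome, completers-only t-test on week-16 values, no true effect.**

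| Dropout control / CT | Correlation of dropout with outcome | Spurious difference (SD) | Type I error |
|---|---|---|---|
| 20% / 20% | 0.5 | 0.00 | 0.048 |
| 10% / 30% | 0 | −0.01 | 0.053 |
| 10% / 30% | 0.5 | 0.16 | 0.086 |
| 10% / 50% | 0.5 | 0.30 | 0.158 |

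Here bias needed both unequal loss and loss related to outcome. Equal loss still costs power: for a 0.8 SD effect, power falls from 0.83 to 0.74 with 20% dropout in each arm.

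**3. Precision.** Let ρ be the correlation between baseline and week 16, with unit SD and complete data. Per-person variance is 1 for a raw week-16 comparison, 2(1 − ρ) for a change score and 1 − ρ² when baseline is a covariate. The last two have the ratio (1 + ρ)/2.

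- ρ = 0.65: (1 + 0.65)/2 = 0.825, so 17.5% lower than the change score; ρ² = 0.4225, so 42% lower than raw.
- ρ = 0.75: (1 + 0.75)/2 = 0.875, so 12.5% lower than the change score; ρ² = 0.5625, so 56% lower than raw.

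These formulas ignore dropout, the week-8 value and the cost of estimating the model. Simulation of 20 versus 40 with between-visit correlations of 0.65 to 0.75, covering no, equal and unequal dropout, gave about 14-20% lower variance than the change score and 34-41% lower than the raw comparison. The gain is present with no dropout at all.

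**The case against.** Several counter-arguments have force.

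- *Intention-to-treat often means only analysis by assigned group, and a t-test can be run on imputed values.* True. The named tests are not inherently incompatible with the principle. But no imputation or analysis set is given, so as written they run on observed data.
- *The plan never says that a short calendar counts as a full one.* Correct. A reader might infer it from the raw count, but the text is silent, and excluding incomplete calendars fits it equally well.
- *Stopping the intervention is not stopping follow-up.* This also stands. Calendars and assessments run on their own schedule, sessions are equal in number, and both arms get tracking and reminders. Retention could be better in CT.
- *The falls bias is small beside the noise.* With an assumed 1.5 falls per person-year, the 16-week mean is 1.5 × 16/52 = 0.46. The SE of the log ratio is √[(1/20 + 1/40)(1/0.46 + 1)] = 0.49, and the 95% interval spans a factor of exp(1.96 × 0.49) = 2.6 each way. A ratio of 0.89 is about 0.24 SE from no effect. The distortion is in one direction, however, and can be avoided.
- *A count model is not better calibrated.* In 2,000 simulated trials a negative binomial Wald test with offset had type I error of 4.9-5.6% at mean 0.46 but 5.5-7.9% at mean 1, where Mann-Whitney gave 4.7-5.9%. This is why the rate ratio is proposed beside the Mann-Whitney test and not in its place.
- *The aim is exploratory, and mixed models are already planned.* This lowers the urgency and the cost of the change. It does not supply the missing rule.

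**Conclusion.** The gap is real: intention-to-treat is stated without a rule for missing week-16 values or incomplete calendars, and the named tests use neither days at risk nor all the data collected. Differential dropout could bias the fall comparison. For the t-tests, the dropout must also be related to outcome.

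Three stronger readings are not supported.

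- Dropout does not bias the comparison as such. Equal dropout left the fall ratio at about 1.00.
- The bias need not favour CT. It was about 0.89 at 10%/30% and about 1.12 at 30%/10%.
- A bias of 0.18 SD can be produced for a raw week-16 comparison (25% CT dropout related to the week-8 value, none in control), but it does not carry over to fall risk. That outcome is defined as change from baseline, and the change-score bias in the same setting was 0.01 SD.

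The firmest gain is in precision: about 14-20% lower variance than a change-score t-test, and about 34-41% lower than a raw one, under assumed correlations of 0.65 to 0.75. All dropout rates, fall rates and correlations are assumptions. The change is worth making, but an exploratory trial of 60 does not stand or fall on it.

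**What to change.** 1. Define the analysis set as all randomised participants by assigned arm, and state how missing outcomes and incomplete calendars are handled.
2. For continuous outcomes measured repeatedly (fall risk, gait, sway, disability), make the planned linear mixed model the main between-group analysis. Include everyone with any data, with baseline, arm by visit, and the week-16 contrast as the estimate. Keep the t-test or Mann-Whitney as sensitivity analyses. The CANTAB row of Table 2, as it reads here, marks only the allocation visit, so its schedule must be confirmed before the same model is used for cognition.
3. For falls, count observed calendar days. The daily letter lets a blank day be told apart from a fall-free one. Report a rate ratio with log observed days as offset, using partial calendars, alongside the Mann-Whitney test, which could be applied to falls per observed day.

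The cost is SAP wording and no new data. The downsides are a missing-at-random assumption, a model slightly harder to explain, and imperfect small-sample calibration of a count model at 20 versus 40.

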Falls and Injurious Falls	Self-Report (Prospective Fall Calendar)
SECONDARY OUTCOMES	
Fall Risk	10M Walk Test 90 Second Balance Test
Cognition Speed of Processing & Response Time Attention Working Memory Task Shifting Planning and Decision Making	CANTAB Simple Response Time Rapid Visual Information Processing Verbal Recognition Memory Spatial Working Memory Intra-Extra Dimensional Set Shift

	Cambridge Gambling Task One Touch Stockings of Cambridge Stop Signal Test
Quantitative Gait and Turning Measures Gait speed (m/s) cadence (steps/min) stride length (m) turn duration (s) turn peak velocity (m/s)	APDM Inertial Sensors Walking trials under testing conditions of: Usual Pace 4-Meter walking laps x 4 Usual Pace 7-Meter walking laps x 2 (if space allows) Fast Pace 4 or 7-Meter walking laps x 2 (space dependent)
Postural Balance Measures: (medial heel-to-medial heel distance = 10 cm) ISway JERK (m^2/s^5) ISway PATH (m^2/s^2) ISway Mean velocity (MV; m/s) ISway Root mean squared (RMS; m/s^2)	APDM Inertial Sensors (ISway): (Inertial sensor at 5 th lumbar level) Static Standing 30-second trials under six conditions: normal base-firm, eye open and eyes closed; narrow base-firm, eye open and eyes closed; normal base, foam surface, eye open and eyes closed
Disability	Gill Disability Scale

Study Design

The design is a two-group randomized controlled trial following a 1-week run-in procedure comparing 16-weeks of a web-based CT intervention to attention control (See Table 2).

Baseline Visit (-T1)

If eligible for inclusion after the in-person screening, the research staff member discusses the project in detail with the individual to ascertain interest in further participation and to allow for provision of informed consent. Following informed consent, the baseline visit commences. At this visit, participants are asked about a) demographics (age, gender, race/ethnicity, formal education, income level, insurance status); b) pre-existing conditions (Charlson method); c) current medications (brown bag method). Questionnaires are administered to participants at baseline to assess: 1) social support (MOS Social Support Survey) and 2) functional status (Gill Disability Scale). Participants undergo an assessment of cognitive abilities using the Cambridge

Table 2. Study Protocol (*denotes data are collected, but is secondary outcome)

	Study period							
		Enrollment	Allocation	Post-allocation				Exit

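### The only covariate provision is a sensitivity analysis triggered by a baseline significance test on demographics; prognostic covariates should be pre-specified instead

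*Combined protocol and SAP*

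**What the plan says.** All references are to the combined protocol and SAP.

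- **Covariate rule (ANALYSIS, first paragraph).** The trigger is "Should there be significant differences between groups on baseline demographic variables despite randomization"; the consequence is that "we will examine the relationship between the variable and the outcome using sensitivity analyses". No test is named for the baseline comparison and no method for the sensitivity analysis. The only significance level given is general: "A value of $p<0.05$ will be considered statistically significant".
- **Main comparisons (ANALYSIS, second paragraph).** Falls and injurious falls are compared by Mann-Whitney U, fall risk (change from baseline in 10M walk speed and balance score) by Student's t-test, and the other secondary endpoints by one or other of these tests. Linear mixed models are exploratory. No covariate is named for any of them.
- **Allocation (Run-in and Allocation).** 20 control and 40 cognitive training participants, in blocks of 6, with no stratification factor named.
- **Baseline data (Baseline Visit, Table 2).** Six demographics are recorded: insurance, income, education, race/ethnicity, gender and age. The trial also records "b) pre-existing conditions (Charlson method); c) current medications (brown bag method"), social support, disability, cognition, 10M walk, 90-second balance, sensor gait and sway, SPPB and TUG. The rule covers only the six demographics.

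**The concern.** Under proper randomisation any baseline difference is due to chance, so a significance test of it carries no information on whether the variable should be in the model. What matters is how strongly the variable predicts the outcome, and that can be judged before any data are seen. The rule therefore goes wrong in two ways. It can pass over a moderate imbalance in a strong predictor because 60 people are too few to make it significant. It can also fire on a variable that has nothing to do with falling.

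Its scope adds to the problem. The variables most likely to predict walking, balance and falls in this population are the baseline physical measures and comorbidity, and none of them can trigger anything. With no stratification and no adjusted model, neither the design nor the main analysis uses this information, apart from the change-score definition of fall risk. At stake are the precision of the secondary comparisons and their interpretation when the groups happen to differ on a strong predictor.

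**Working it through.** The plan states no power, effect size or SD, so it has no figure of its own to reproduce.

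**Inputs from the plan:** n = 20 and 40; significance level 0.05; six demographics.

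**Assumptions:** two-sided tests; a pooled t-test for a continuous baseline variable; full numbers with no dropout; covariate-outcome correlation ρ of 0.3, 0.5 or 0.7. Everything below is normal theory for continuous variables. None of it is a calculation for fall counts under Mann-Whitney.

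**1. Where the flag trips.** Standard error of a standardised difference = √(1/20 + 1/40) = 0.274. Smallest significant difference = t(0.975, 58 df) × 0.274 = 2.002 × 0.274 = 0.548 SD. With 18 versus 36 it would be 0.579 SD.

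**2. How often a noticeable imbalance is missed.** P(|d| > 0.3 SD) = 2[1 − Φ(0.3/0.274)] = 0.273. Taking off the 0.05 that is flagged leaves about 0.22 per variable. The median absolute imbalance is 0.6745 × 0.274 = 0.185 SD.

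**3. How often the rule fires by chance.** With six independent tests at exactly 5%: 1 − 0.95⁶ = 0.265. This is an upper figure. Several of the six variables are categorical, and Fisher's exact test on a binary variable at 20 versus 40 has an actual size of only about 2.8% to 3.6% (prevalence 10% to 70%). Positive correlation among education, income and insurance would lower it further.

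**4. Conditional effect of an imbalance d on an unadjusted comparison.** Bias = ρd. Given d, the unadjusted statistic is distributed as N(ρd/0.274, 1 − ρ²).

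| ρ | Bias at d = 0.3 | Conditional type I error | Bias at d = 0.548 | Conditional type I error |
|---|---|---|---|---|
| 0.3 | 0.09 SD | 5.2% | 0.16 SD | 8% |
| 0.5 | 0.15 SD | 5.3% | 0.27 SD | 13% |
| 0.7 | 0.21 SD | 4.7% | 0.38 SD | 22% |

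**5. Unconditional validity.** In 40,000 simulated trials of 20 versus 40 per value of ρ, type I error was 0.049 to 0.051 for the unadjusted test and 0.050 to 0.051 for ANCOVA in every trial.

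**6. Precision gained by pre-specified adjustment.** Detectable effect at 80% power = (1.96 + 0.84) × 0.274 × √(1 − ρ²).

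| ρ | Detectable effect | Power at 0.5 SD |
|---|---|---|
| 0 (unadjusted) | 0.77 SD | 45% |
| 0.3 | 0.73 SD | 48% |
| 0.5 | 0.66 SD | 56% |
| 0.7 | 0.55 SD | 72% |

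**7. Change scores.** With equal variances σ² and baseline-to-follow-up correlation r, the variance of change is 2σ²(1 − r) and the ANCOVA residual variance is σ²(1 − r²). Their ratio is (1 + r)/2: 0.65, 0.75 or 0.85 for r = 0.3, 0.5 or 0.7. A baseline imbalance d biases the change score by (r − 1)d; at r = 0.5 and d = 0.5 that is −0.25 SD.

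**The case against.** The strongest defence is that nothing in the plan is invalid. The main tests are fixed in advance, the trigger adds only a supplementary analysis, and the trial is described as exploratory. That stands, and it limits the point to efficiency and interpretation. Four stronger readings that a reader might infer fail for related reasons.

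- **That chance decides which analysis is used.** It does not. The tests are named and nothing switches; chance decides only whether a sensitivity analysis is added.
- **That 0.55 SD is the limit of what goes unadjusted.** It is only the point at which a continuous demographic is flagged. The main comparisons are unadjusted at any imbalance, and the physical measures and comorbidity have no threshold at all.
- **That type I error is inflated.** Unconditionally it is about 5%. At a 0.3 SD imbalance even the conditional rate stays near 5%.
- **That a shift of about 0.25 SD is typical.** It needs ρ = 0.5 and d = 0.5. Imbalances between 0.5 and 0.548 SD arise in about 2% of trials per covariate; at the median imbalance the shift is about 0.09 SD.

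It can also be said that the triggered step may mean re-estimating the group effect with the variable included. The wording permits that but does not commit to it, so the fair criticism is that the step is unspecified.

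Finally, defining fall risk as change from baseline does take partial account of baseline walk and balance. Step 7 shows that it is not equivalent to adjustment.

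**Conclusion.** The point holds as one of lost precision and conditional bias. The plan's sole covariate provision rests on the wrong criterion, omits the baseline variables most likely to be prognostic, and leads to an undefined analysis. For continuous outcomes, the gain forgone is a fall in the detectable effect from about 0.77 SD to between 0.73 and 0.55 SD, depending on a correlation that the documents do not give. For outcomes analysed as change, ANCOVA variance would be 65% to 85% of the change-score variance for r between 0.3 and 0.7.

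These sizes rest on normal theory, equal variances and full follow-up. They do not carry over to the fall counts, for which no gain has been computed. The change is worth making because it is nearly free for the continuous outcomes, but the planned tests would remain valid without it.

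**What to change.** 1. Delete the significance-triggered rule, and present baseline data descriptively without p-values.
2. For each continuous secondary outcome with a baseline measurement, pre-specify ANCOVA (or the mixed model) adjusting for the baseline value of that outcome and age, whatever imbalance is observed. Report the unadjusted comparison as the sensitivity analysis.
3. For falls and injurious falls, keep the Mann-Whitney test, which takes no covariates. If the plan separately adopts a count model, pre-specify age and baseline walk speed or balance as its covariates.

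**Cost.** The data are already collected. Items 1 and 2 need revised SAP wording, one or two degrees of freedom and slightly more analysis work. A count model for falls would change the primary test, so it is a separate decision and more than a wording change.

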Study Protocol/Statistical Analysis Plan
Evaluating Technology-Based Fall Prevention Interventions
NCT03190460

9/27/2016

Objectives

The primary study objective is to explore the effectiveness of a 16-week cognitive training (CT) intervention to reduce risk and incidence of fall in community-dwelling older adults at risk for fall. Additional objectives of the study are to explore the effectiveness of a CT intervention on cognition and functional outcomes and to examine the feasibility and acceptability of the study protocol and intervention in this population.

Outcomes

Primary Outcome. At time of allocation, participants will be provided with a Monthly Fall Calendar and instructed in its use. At the end of each day participants are asked to place one of 3 letters in the box for the day: "N" for no fall; "F" for fall; and "I" for fall resulting in an injury), considered the "gold-standard" for falls assessment (See Table 1). For purposes of this study, a fall was defined as an "unintentional". For individuals who experience multiple falls in a single day, they are asked to denote the number (ex. "F-2"). Fall calendars will be collected monthly (See Table 2), and a new calendar provided to the participant during the study period. The time period for primary outcome assessment is falls over the period of 4 months. For any fall resulting in injury, we will request permission from the participant to obtain medical records for any treatment sought at time of injury.

Secondary Outcomes. Of interest as a secondary outcome in this study is reduction in risk of fall at the end of the 16-week intervention (See Tables 1 and 2). This is defined by 1) an increase in the 10M walking speed from baseline or 2) an increase in the Balance test score from baseline.⁴⁰ As secondary endpoints, we will measure cognitive outcomes (using the Cambridge Neurological Assessment Battery [CANTAB]), additional gait and postural sway measures (using body-worn inertial sensor system, the APDM Mobility Lab, Portland, OR; See Tables 1 and 2), and disability (Gill Disability Scale). We will explore if there is retention of benefit of the intervention on fall risk, gait, balance and cognitive outcomes one month following end of the intervention. Feasibility and acceptability of the study protocol and CT intervention will also be evaluated.

Table 1. Summary of Outcome Measures and Source of Measurement

Measure	Source (Instrument/Test[s])
PRIMARY OUTCOME	

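### The plan tests falls and injurious falls but does not estimate the effect on fall rate, and it has no rule for partly returned calendars

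*Combined protocol and SAP*

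**What the plan says.** The combined protocol and SAP states its aim under Objectives as "to reduce risk and incidence of fall in community-dwelling older adults at risk for fall". Table 1 lists "Falls and Injurious Falls" as the primary outcome, and the ANALYSIS section repeats it: "The primary outcome of interest in the proposed RCT is reduction number of falls and injurious falls". The method follows directly: "Number of falls and injurious falls will be determined from fall calendar data. Between group differences will be assessed using Mann Whitney U test".

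The data source is a daily diary. Under Outcomes: "At the end of each day participants are asked to place one of 3 letters in the box for the day" (no fall, fall, or fall with injury). Also: "Fall calendars will be collected monthly (See Table 2), and a new calendar provided to the participant during the study period".

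Beyond the test, the ANALYSIS section gives an intention-to-treat statement, a 0.05 threshold, a sensitivity analysis if baseline demographics differ, and a descriptive element: "means, standard deviations and distributions will be used to describe the outcomes of interest". Its feasibility paragraph expects some participants to drop out and plans to describe them. No dropout rate, fall rate, effect size or power figure appears anywhere.

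**The concern.** An aim about incidence calls for events per unit of observed time, compared between arms, with a measure of uncertainty. A rank test on raw numbers shows whether the two distributions differ. It does not say by how much the fall rate differs, or how well that difference is known. With 40 against 20 participants, a non-significant result is likely even if CT halves the fall rate. Without an interval, a reader could not tell evidence of no effect from too little evidence.

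The second gap is the calendar. A participant who stops after six weeks contributes fewer opportunities to record a fall. Taken as it stands, that count is ranked as though it covered all 16 weeks. Intention-to-treat says who is analysed, not how a short calendar is counted, so that decision is left open until the data are in.

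**Working it through.** **1. The plan's own figures.** There is no power calculation to reproduce. The arm sizes are consistent: 60 / 6 = 10 blocks, each 2 control and 4 CT, giving 20 and 40.

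**2. What the plan supplies for the primary outcome.** Between-group test: yes. Group descriptives: yes. Rate ratio, confidence interval, person-time denominator, rule for missing calendar days: none in any section. The first mixed-model sentence concerns fall risk, defined by walking speed and balance score. The second follows the list of secondary endpoints.

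**3. Assumptions for the illustrations.** The documents give no rates, so ranges are used. Counts are gamma-Poisson with control means of 0.4 / 0.8 / 1.2 falls per person per 16 weeks and dispersion *k* of 1 or 4 (variance = mean + *k* x mean squared). Dropout times are uniform over the 16 weeks. The test is two-sided at 0.05 (sidedness is not stated in the plan), tie-corrected, on partial counts as they stand. Runs are 4,000 trials per scenario unless stated.

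**4. Effect of unequal calendar loss on the raw counts, no true effect.** Mean fraction of time observed = 1 - dropout x 0.5.
- CT 30%: 1 - 0.15 = 0.85. Control 10%: 1 - 0.05 = 0.95.
- Ratio of mean counts = 0.85 / 0.95, about 0.89.
- Ratio of falls per person-time = (0.85 / 0.85) / (0.95 / 0.95) = 1.00.

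**5. Size of Mann-Whitney for falls, no true effect.**
- Dropout 0/0, 20/20, 30/10 and 10/30% (CT/control): 4.4-6.5% overall.
- At 30% against 10%, the rejections are lopsided: 4.4-5.1% favour CT and 0.9-1.2% favour control.
- At 40% against 5%, *k* = 1, 100,000 trials per setting: 6.9 / 8.1 / 8.9%. At *k* = 4: 5.9 / 6.8 / 6.6%.
- A harsher pattern, with 30% of CT and none of control stopping a quarter of the way through (*k* = 1), gives 9.2% and 11.2% at control means 0.5 and 1.0.

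**6. The interval that the plan omits (falls, true ratio 0.5, no dropout).** SE(log ratio) = sqrt[(1/m0 + k)/20 + (1/m1 + k)/40], where m0 and m1 are the control and CT means.
- For m0 = 0.8, m1 = 0.4, *k* = 1: sqrt(2.25/20 + 3.5/40) = sqrt(0.200) = 0.447.
- 95% CI = 0.5 x exp(±1.96 x 0.447) = 0.21 to 1.20.

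| Control mean | *k* = 1 | *k* = 4 |
|---|---|---|
| 0.4 | 0.16-1.53 | 0.12-2.14 |
| 0.8 | 0.21-1.20 | 0.14-1.79 |
| 1.2 | 0.23-1.09 | 0.15-1.68 |

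Mann-Whitney power in the *k* = 1 column is 22 / 28 / 33%.

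**7. Injurious falls (assumed control means 0.05 / 0.10 / 0.20, no dropout).** An arm of *n* has no events with probability (1 + k x mean)^(-n/k). At *k* = 1, mean 0.05 and no effect: control 1.05^-20 = 0.377, CT 1.05^-40 = 0.142. The chance that at least one arm is empty is 1 - 0.623 x 0.858 = 0.47. Across the three means it is 47 / 17 / 3% with no effect and 61 / 27 / 5% at ratio 0.5. Maximum likelihood then gives no finite ratio, which is why this half of the outcome needs an exact interval. That interval covers 96.4-99.9% at *k* = 1 and 92.4-99.9% at *k* = 4.

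As a test it is weaker: at ratio 0.5 and *k* = 1, its power is 1 / 5 / 12% against 10 / 12 / 14% for Mann-Whitney, whose size here is about 3-6%.

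**The case against.** Four arguments favour the plan as written.

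- **It does not promise only a p-value.** A reader might infer that nothing else will be reported. The text never says so, and group means over a fixed window would allow a crude ratio. This stands, and the point is limited to what is specified for inference. A crude ratio would still have no interval and no allowance for days observed.
- **The test suits the outcome.** A rank test on skewed counts over a fixed period is a recognised choice. A reader might infer that it is biased here. The documents do not support that: both arms have the same number of sessions, tracking and reminders, participants are not told their condition, outcome assessors are blinded, and calendars are collected monthly. Nothing clearly suggests that loss will differ by arm.
- **A different primary test is a matter of preference.** This largely stands. For falls, a person-time negative binomial score test with a within-block permutation p-value gains only 0-8 points of power with no dropout (*k* = 1: 22 / 33 / 41% against 22 / 28 / 33%). For injurious falls, the figures above argue against replacing Mann-Whitney with the exact test.
- **The trial is exploratory and the intervals would be inconclusive.** They would be wide. But the width is itself a result, and it tells the designers of a later trial which effects remain plausible.

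**Conclusion.** The point holds in a limited form and is a cheap improvement. It is certain from the text that the primary outcome has a test but no specified effect estimate, interval, exposure denominator or rule for incomplete calendars, for falls or injurious falls.

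The consequences are conditional. If calendar loss is equal, the test keeps its size and the only loss is the missing estimate. If loss differs moderately, the raw-count comparison tilts toward the arm observed for less time, by about 11% in the mean-count ratio at 30% against 10% dropout, while overall size barely moves. Clear inflation needs extreme differences. The fall, injury, dropout and dispersion figures are all assumptions. The comparison of power for injurious falls is for dispersion 1.

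**What to change.** Add the following to the ANALYSIS section.

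- **Falls.** In all randomised participants with any calendar data, over the 16 weeks after allocation, fit a negative binomial model with treatment as factor and log(calendar-days observed) as offset. Report the rate ratio with a 95% profile-likelihood interval, and days observed by arm.
- **Injurious falls.** Report events and person-days by arm and the exact conditional rate ratio with a 95% interval. Take Clopper-Pearson limits for CT's share *p* of all events and convert them by ratio = [p/(1 - p)] x (control days / CT days). Give a one-sided limit if one arm has no events, and counts only if neither has any.
- **Calendar rule.** A day is observed if it carries an N, F or I entry. Repeat the analysis with blank days inside a returned calendar counted as N.
- **Test.** Mann-Whitney may stay as the planned test, and should stay for injurious falls. A permutation p-value for falls, re-randomising within the blocks of 6, is optional. Ranking falls per observed day is not a full substitute, because a zero ranks the same however short the calendar.

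The cost is SAP wording and a little more analysis; the daily entries already supply days observed. The downsides are a model assumption, wide intervals, and profile coverage slightly below 95% at high dispersion (92.8-95.3% across scenarios at ratio 0.5). The exact interval is conservative when events are very sparse and somewhat narrow if injuries cluster in few people. The offset also corrects only partly if frequent fallers drop out more. With above-median fallers 2-3 times as likely to leave (30% CT against 10% control, no effect), the person-time ratio is 0.97-0.96 against 0.87-0.86 for mean counts.
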